4.2.2 Stopping Criteria

4.2.2.1 Individual Subjects

Subjects will be withdrawn from the study on safety grounds to be established by the DSMB and as per section 5.4.1.

4.2.2.2 Study as a Whole

The DSMB will establish criteria for stopping the study. If the criteria are met, a substantial amendment will be filed, and the study will be stopped temporarily, and the events investigated to determine if they are related to the investigational medicinal product (IMP). If it is determined that the events are related to the IMP, the study will be stopped, and the Health Authorities and ethics committees informed.

4.2.3 Independent Data and Safety Monitoring Board (DSMB)

An independent DSMB comprising experts in drug safety, biostatistics and other relevant fields will be established by the sponsor to assess the progress of the trial, the safety data and efficacy endpoints. Stopping criteria for individual subjects and the study will be established.

The composition, responsibilities and procedures of the Board will be documented prior to the commencement of the study and randomisation of the first subject. Recommendations of the Board and actions taken by the sponsor will be documented.

5 POPULATION

500 subjects diagnosed with IBS will be enrolled into the study. Diagnosis of IBS will be defined by the Rome IV criteria and must be met for the last 3 months with symptom onset at least 6 months prior to diagnosis.

IBS patients will be screened based on the inclusion and exclusion criteria described in 5.1 below, and will be classified into one of the following Cohorts according to the Rome IV classification of IBS subtypes.

Cohort C: 250 subjects diagnosed with IBS-C

Cohort D: 250 subjects diagnosed with IBS-D

5.1 Inclusion Criteria

All subjects must meet all the following inclusion criteria:

- 1. Written consent on an Institutional Review Board (IRB)/ Independent Ethics Committee (IEC) approved ICF before any study specific evaluation
- 2. Males and Females between 18 and 70 years of age
- 3. Body Mass Index (BMI): 18-39 kg/m²
- 4. Having IBS-C or IBS-D as defined by Rome IV, including Subtype Classification as defined per Table 2

Recurrent abdominal pain on average, at least 1 day/week in the last 3 months associated with two or more of the following criteria:

• Related to defecation

- Associated with a change in frequency of stool
- Associated with a change in form (appearance) of stool

The above criteria must be met for the last 3 months with symptom onset at least 6 months prior to diagnosis.

IBS-C and IBS-D subtypes will be further classified as follows:

Table 3:

IBS-C	IBS-D
□ Abdominal Pain Intensity: weekly average of worst daily (in past 24 hours) abdominal pain score of > 3.0 on a 0 to 10-point scale	\Box Abdominal Pain Intensity: weekly average of worst daily (in past 24 hours) abdominal pain score of > 3.0 on a 0 to 10-point scale
	And
And	
□ Stool Frequency: more than 25% of bowel movements with a consistency of Type 1 or Type 2 Bristol stool chart and less than 25% of bowel movements with Bristol stool form Type 6 or Type 7. Subject must have fewer than 3 CSBMs ¹ within a one week period (7 days)	□ Stool Consistency: more than 25% of bowel movements with a consistency of Type 6 or Type 7 Bristol stool chart and less than 25% of bowel movements with Bristol stool form Type 1 or Type 2. Subjects must have at least one Type 6 or Type 7 bowel movements on at least four days within a one week period (7 days).

*Stool types based on Bristol Stool Chart; Hard stools -Type 1 and 2; Soft stools – Type 6 and 7 (see Appendix 3). Source: (https://irritablebowelsyndrome.net/clinical/new-rome-iv-diagnostic-criteria/) (see Appendix 6) ¹ CSBM defined as a bowel movement that is both complete and spontaneous. Bowel movements where laxative use is recorded in the concomitant medication questions in a 24 hour period, by IBS-C subjects will not be counted as CSBMs when subtyping for randomisation.

- Have a moderate or severe IBS symptom severity score ; ≥175 at the screening visit as defined by IBS-SSS. A tolerance of -10% (≥ an IBS-SSS score of 157.5) will be allowable at the Baseline (Visit 1).
- 5.2 Exclusion Criteria

Any of the following criteria will exclude the Subject from study participation:

- 1. Males or females <18 and >70 years of age
- 2. Have an IBS symptom severity score < 175 as defined by IBS-SSS
- 3. BMI: $<18 \text{ or } >39 \text{ kg/m}^2$
- 4. Have a significant acute or chronic coexisting illness (cardiovascular, gastrointestinal, endocrine, immunological, metabolic or any condition which contraindicates, in the investigators' judgment, entry to the study)
- 5. Confirmed clinical diagnosis of bile acid malabsorption and / or on medication for bile acid malabsorption

- 6. Individuals who, in the opinion of the investigator, are poor attendees or unlikely for any reason to be able to comply with the study requirements
- 7. Patient is currently enrolled in or has not yet completed at least 30 days since ending other investigational device or drug study(s), or patient is receiving other investigational agent(s)
- 8. Have an active or recent (within 3 years) malignant disease or any concomitant end-stage organ disease. A non-melanoma skin cancer that has been adequately treated with no recurrence within 3 months of screening is not excluded.
- 9. Females who are pregnant or breast feeding
- 10. Refusal to use acceptable methods of birth control (true abstinence, sterilisation, birth control pills, injections or contraceptive implants) for women of child bearing potential while on treatment and following completion of 2 menstrual cycles/ months after the last dose of study treatment. For Males, a barrier method of birth control from randomisation until the Follow-Up visit, unless vasectomised
- 11. Use of antibiotics within 30 days of screening
- 12. Use of systemic steroids within 30 days of screening
- 13. Change in dose or introduction of an antipsychotic within the last month
- 14. Have suffered from an uncontrolled or current major psychiatric disorder
- 15. Clinically diagnosed Lactose intolerance
- 16. Clinically diagnosed Coeliac disease
- 17. Change of diet e.g. FODMAP, gluten-free within last 3 months
- 18. Those > 50 will be excluded if their diagnosis of IBS is recent (<12 months) and if they have not had a sigmoidoscopy or colonoscopy within previous 5 years.
- 19. Any GI related abdominal surgery other than hernia repair or appendectomy. Cholecystectomy more than 6 months previously is not an exclusion
- 20. Subjects taking prucalopride
- 21. Known HIV infection, or hepatitis A, B, or C active infection
- 22. Subjects with abnormal laboratory values at screening deemed by the investigator to be clinically significant
- 23. Subjects who have taken commercially available probiotics within the last month (30 days prior to randomisation). See Appendix 7
- 24. Subjects with known or suspected hereditary fructose intolerance, glucose-galactose malabsorption or sucrase-isomaltase insufficiency
- 25. Subjects taking guanylate cyclase agonists; such as linaclotide and lubiprostone

5.3 Treatment assignment procedures

5.3.1 Randomisation

This is a double-blind study and subjects will randomly receive either Blautix[™] or placebo in a 1:1 ratio respectively. At Baseline (Visit 1), subjects will be classified into either the IBS- C (Cohort C) or the IBS-D (Cohort D) cohort of subjects and 250 subjects will be enrolled into each cohort. Within each cohort, 125 subjects will randomly receive Blautix[™] and 125 subjects will randomly receive matching placebo. Allocation of randomisation numbers will be performed centrally using an interactive voice/web response allocation system (IV/WRS).

Subjects, 4D pharma Plc, designated CRO and clinical site staff will be blinded to the investigational product allocation for each subject. Randomisation data will be kept strictly confidential, filed securely by the Sponsor (or designee) and accessible only to authorised persons of the Sponsor (or designee), and accessible only to authorised per Sponsor (or designee)'s standard operating procedures (SOPs) until the time of unbinding.

5.3.2 Blinding Procedures

The blinding will be maintained using placebo capsules comparable in appearance to the Blautix[™] capsules.

5.3.3 Subject Numbering

The investigators must maintain a screening log of all screened subjects and those randomised into the study.

Each subject will be given a unique identification subject number, to facilitate anonymous identification within the study. Once assigned to a subject, a subject number will not be re-used.

5.3.4 Emergency Unblinding Procedures

The IV/WRS will be used for emergency unblinding of the treatment codes. The treatment codes should not be broken except in medical emergencies when the management of the subject requires knowledge of the treatment randomisation. The investigator must sign and date the code break form supplied and document the reason for breaking the code. The Sponsor Medical Monitor should be informed as soon as possible and within 24 hours of the event.

In addition, each subject will be given a card and asked to carry it with them at all times in case of an emergency. The card will include the study number, subject number, Investigational product and the name and 24-hour telephone number of the investigative site. Subjects should be asked to return this card at the end of the study.

The Sponsor's pharmacovigilance provider may break the code for serious adverse events that are unexpected and are suspected to be causally related to the investigational product and potentially require expedited reporting to the regulatory authorities.

5.4 Subject withdrawal

5.4.1 Reasons for Withdrawal

Subjects have the right to withdraw from the study at any time and for any reason without prejudice to future medical care by the investigator or at the institution.

Reasons for removal from the Protocol-required investigational product(s) or procedural assessments might include:

- Withdrawal of informed consent
- Pregnancy
- Investigator's opinion that it is in the best interests of the subject

[figure not shown]
• Safety concern (due to an AE, Failure to follow contraception, and/or protocol requirements)

If a subject withdraws from the trial prematurely, the Investigator must determine the primary reason for this and record it in the CRF. If possible, subjects who withdraw from the study after the start of dosing and before completion should be seen by an Investigator and undergo the assessments and procedures scheduled for the follow-up visit. For subjects who are lost to follow-up, the investigator should show due diligence by documenting in the source documents all steps taken to contact the subject.

5.4.2 Replacement of Subjects

Subjects who are withdrawn from the study by the Investigator due to adverse events will not be replaced. Subjects who withdraw for any reason before the first dose or for reasons other than adverse events after the start of dosing may be replaced.

6 INVESTIGATIONAL PRODUCTS

6.2 Dosage, Frequency and duration of Dosing

Subjects will be randomly assigned at Baseline (Visit 1, Day 1) to 1 of 2 treatment groups, as follows:

Blautix[™] or placebo capsules will be administered twice daily at approximately 12 hourly intervals; morning and evening; approximately 30 minutes before food for a duration of 8 weeks. CCI

supplied with enough treatment supply at the Baseline Visit to last until the next scheduled Clinic Visit and then at subsequent visits.

The Pharmacy manual will include further detail regarding treatment storage and dosing guidelines.

6.3 Packaging and Labelling

Packaging and labelling will be in accordance with Good Manufacturing Practice Annexe 13 requirements and released by a Qualified Person (QP) in accordance with the Clinical Trials Directive 2001/20/EC and GMP Directive 2003/94/EC for Investigational Medicinal Products.

6.4 Storage and Expiry

Shelf life will

be assigned in accordance with emerging stability data.

Arrangements will be made for subjects to transport their capsules in cool boxes between the study site and their home.

6.5 Treatment Compliance

Subjects will be asked to take their study medication (2 capsules twice daily) at approximately 12 hourly intervals from their first dose, approximately 30 minutes before food. They will record the time that they took their medication in their smartphone which will be supplied to them at Screening. Doses will be taken in the morning two (2) capsules approximately 30 minutes before breakfast and in the evening two (2) capsules approximately 30 minutes before the evening meal. Subjects will be asked not to open the capsules, CCI and to return any unused capsules.

6.6 Accountability

An accountability record must be maintained at the Investigator site to record the date and number of capsules, received, dispensed to subjects, returned from subjects and not used.

At the end of the study, a full reconciliation must be documented and checked by the Monitor from the Sponsor. Supplies must be retained at the Investigator site until instructions for return and destruction are provided by the Sponsor.

6.7 Permitted Dose Adjustments and Interruptions

No dose adjustments or interruptions will be permitted. Treatment should be withdrawn in subjects who are unable to tolerate it.

6.8 Concomitant Treatment

Any concomitant medication taken within 30 days prior to the first dose of study medication and up to the follow-up visit should be recorded in the case report forms.

6.9 Prohibited Medication

Probiotics such as yogurts, yogurt-type drinks and other soft drinks e.g. fruit juices may be taken during the study. Probiotic supplements formulated as capsules or sachets are prohibited. Acceptable probiotics taken during the month before screening should be continued through the study period and to follow-up to ensure consistency.

Prucalopride is a prohibited medication and should not be taken during the study.

IBS-C subjects should not take guanylate cyclase agonists (such as linaclotide) and lubiprostone. IBS-D subjects should not take bile acid sequestrants (such as cholestyramine, colestipol, colesevelam), 5-hydroxytryptamine (serotonin) 3 receptor antagonists (such as alosetron), rifaximin and eluxadoline (see Appendix 7).

Subjects are not eligible for the study if they have received antibiotics or systemic corticosteroids within 30 days prior to the screening visit. Subjects on inhaled steroids for asthma may be included but oral or infused steroids for asthma are not permitted. If these medications are required during the study, the subject does not need to be withdrawn but details will be recorded in the concomitant medication case report forms.

7 STUDY ASSESMENTS

7.1 Clinical Assessments

Medical History

A medical history including prior and current medication will be obtained during screening. In addition, demographic data will be collected, including gender, race, and ethnic origin.

Physical Examination

A full physical examination will be performed by the Investigator at screening and at study visits as indicated in Table 1. Body weight in kilograms (kg) and height in metres (m) will be measured and the BMI will be calculated.

Vital Signs

Blood pressure, heart rate, respiratory rate and temperature will be taken as indicated in Table 1. Blood pressure and heart rate will be measured in the supine position using an automated blood pressure monitor.

ECG

A 12-lead ECG will be taken as indicated in Table 1. Subjects will be in a supine position prior to recording an ECG. The ECG traces will be reviewed and commented on by the Investigator and the traces signed and dated.

Subject Assessments:

Refer to Table 1: Schedule of Assessments and Procedures. The assessments will be completed by the subject either at home using the smartphone provided or during the clinic visit.

Abdominal Pain Score

Subjects will be asked to rate their worst abdominal pain over the past 24 hours using an 11-point Numeric Rating Scale (NRS) and a weekly average will be recorded. This data will be recorded daily for a 7-day period up to Baseline (Visit 1) to allow Subject to be classified into Cohorts of IBS-C or IBS-D sub-types. Once subjects are randomised they will be asked to record their score daily on their smartphone.

Subjects will respond to the following question: 'How much abdominal pain have you felt today' on a scale from 0 (none) to 10 (worst possible pain)" using an 11-point NRS ranging from 0 (none) to 10 (worst possible pain)?

Subject Global Assessment of Relief

A weekly subject response to the question Please consider how you felt this past week in regard to your IBS, in particular your overall wellbeing and symptoms of abdominal discomfort, pain and altered bowel habit. Compared to the way you usually felt before entering the study, how would you rate your relief of symptoms during the past week?

Using a 5-point Likert scale with the following response options:

Completely relieved; considerably relieved; somewhat relieved; unchanged; worse

Subjects will be asked to record their assessment weekly on their smartphone.

IBS Quality of Life (QOL) (Appendix 1)

Subjects will be asked to complete a quality of life questionnaire consisting of 34 questions with a five-point response. The individual responses to the 34 items are summed and averaged for a total score and then transformed to a 0-100 scale for ease of interpretation with higher scores indicating better IBS specific quality of life. Once subjects are randomised they will be asked to record their score on their smartphone at each clinic visit or within 24hrs prior to the Clinic Visit.

Hospital Anxiety and Depression Score (HADS) (Appendix 2)

Subjects will be asked to complete HADS which is a 14-item scale that generates ordinal data. Seven of the items relate to anxiety and 7 relate to depression. Each item is scored from 0-3 so a subject can score 0 to 21 for either anxiety or depression. Once subjects are randomised they will be asked to complete this questionnaire on their smartphone at each clinic visit or within 24hrs prior to the Clinic Visit.

Bristol Stool Chart

Subjects will be asked to record stool frequency and consistency. Stool types will be based on the Bristol Stool Chart (Appendix 3). This data will be recorded daily for a 7-day period up to Baseline (Visit 1) to allow Subject to be classified into Cohorts of IBS sub-types. Once subjects are randomised they will be asked to record their stool frequency daily up to 10 bowel movements per day and score each stool type on their smartphone. No bowel movements in any given day will also be recorded.

Stool frequency will be defined as a sum of weekly CSBMs. Stool frequency will be recorded using the following question: "How many times did you open your bowels during the past 24 hours? If you have not had any bowel movements today, please enter 0." Subjects will be reminded to rate all of their bowel movements in the Bristol Stool Chart before answering the question. CSBMs will be determined by absence of laxative use recorded in concomitant medication questions for the same 24 hour period.

IBS Symptom Severity Score (SSS) (Appendix 4)

Subjects will be asked to complete a questionnaire on severity of abdominal distension, severity of abdominal pain, frequency of abdominal pain, dissatisfaction with bowel habits, and interference of IBS symptoms with daily life. A score ranging from 0 (no symptoms) to 500 (maximum severity) can be achieved as mild (74-174), moderate (175-299) or severe (>300) IBS symptoms.

The initial data from this questionnaire will be collected during the Screening visit on a tablet device during the clinic visit. This data will be used to classify into Cohorts of IBS sub-types prior to randomisation. Once subjects are randomised, they will be asked to record their responses to the questionnaire on a tablet device during each clinic visit.

Food Frequency Questionnaire (FFQ) (Appendix 5)

Subjects will be asked to complete a questionnaire to obtain frequency information about food and beverage consumption over a specified period of time (day, week and month). FFQ completion at baseline will be in relation to food (s) consumed over the prior 6 months. At each subsequent visit the FFQ shall capture responses to food (s) consumed since last subject visit. Subjects will be asked to complete this questionnaire on a tablet device during each Clinic Visit.

• Concomitant Medications:

Subjects will be asked to record name, dose and time of administration of any medication, other than IMP, taken during the study. This will be reviewed at each visit.

Dosing Diary:

Subjects will be asked to confirm their daily study medication intake by indicating "yes" or "no" to the following questions on the smartphone provided: "Did you take two of your study medication capsules this morning? " in the morning and "Did you take two of your study medication capsules this evening?" in the evening. Subjects will be prompted with reminders via this device.

Diet and Study Restrictions

Dosing should be twice daily at twelve hourly intervals (approximately 30 minutes before breakfast and 30 minutes before evening meal). Subjects with lactose intolerance and Coeliac disease and those with a change of diet within the 3 months before screening are excluded. Subjects taking commercially available supplements (probiotics formulated as capsules or sachets as in Appendix 7) are excluded 1 month (30 days) prior to randomisation and throughout the study to follow-up. Probiotic yogurts, yogurt-type drinks and soft drinks e.g. fruit juices are acceptable if taken during the month before screening and continued to follow-up.

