3.2 Endpoints

Primary Efficacy Endpoint

The primary efficacy endpoint is whether the subject is an overall responder.

A subject is an 'overall responder' if they have reported an improvement in their weekly (Cohort specific) symptoms for \geq 50% of the treatment period (4 out of 8 weeks).

	IBS-C	IBS-D	
Primary Endpoint Responder Symptom Definition	Abdominal Pain Intensity Decrease in weekly average of worst abdominal pain in the past 24 hours score of at least 30% compared with baseline	Abdominal Pain Intensity Decrease in weekly average of worst abdominal pain in past 24 hours score of at least 30% compared with baseline	
	And Stool Frequency	and Stool Consistency (BSS)	
	Increase of 1 or more Complete spontaneous bowel movements (CSBM) per week compared with baseline.	Decrease at least 50% in the proportion of days per week with at least one stool that has a consistency of Type 6 or 7 compared with baseline.	

Secondary Efficacy Endpoints

- Subject global assessment of relief
- Stool consistency/frequency
- IBS-QOL
- IBS-SSS
- HADS

Exploratory Endpoints

Safety Endpoints

- Incidence, nature, severity, relatedness, seriousness, expectedness and outcome of adverse events
- Haematology and blood chemistry assessments
- Vital signs

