#### 10.1.1 Primary Efficacy Endpoint

The primary efficacy endpoint is whether the subject is an overall responder. The definition of an overall responder is IBS subtype specific and consists of two components.

For both IBS subtypes, the first component of overall response is the weekly average of Abdominal Pain Intensity (0-10, 0=none, 10=worst possible pain) over the past 24 hours. Improvement for the week is defined as a decrease of at least 30% compared with baseline.

For the IBS-C subtype, the second component of overall response is the stool frequency per week. Improvement is defined as an increase of 1 or more complete spontaneous bowel movements (CSBMs) per week compared with baseline. The number of bowel movements is recorded once per day in the eCOA device, including zeroes.

For the IBS-D subtype, the second component of overall response is the proportion of days per week with at least one stool with a consistency of Type 6 or 7 on the Bristol Stool Chart. Improvement is defined as a decrease in the proportion of at least 50% compared with the proportion during the 7-day period before baseline used to determine eligibility. Stool consistency is recorded for each bowel movement in the eCOA device, so more than one entry per day may exist. The daily result should be reduced to whether a Type 6 or Type 7 was included on that date.

A subject will be considered a responder only during weeks for which both components indicate improvement. Subjects must have at least 4 evaluable weeks of data as defined in [Section 10.4](#) for each of the instruments used to determine response. Subjects with less than 4 evaluable weeks of assessments available during the treatment period will be considered as non-responders for overall response.

Subjects who have at least 7 evaluable weeks of data and have reported an improvement in their weekly symptoms for  $\geq 50\%$  of the treatment period will be considered overall responders. Subjects who have 4, 5, or 6 evaluable weeks of data must show improvement for  $\geq 60\%$  of the treatment period to be deemed overall responders.

The days for each week will be taken as calendar days from the Day 1 date (randomisation date).

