The denominators for the weekly average of Abdominal Pain Intensity, the stool frequency, and the proportion of days per week with at least one Type 6 or 7 will be the number of days with an assessment during the week. The stool frequency will be multiplied by 7 to convert to a stools per week figure. The stool consistency will be multiplied by 100 to convert to a percentage.

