### 10.2 Baseline Values for Efficacy Assessments

For the daily assessments collected on the eCOA device, baseline values will be derived from the 7 consecutive days assessed preceding the Baseline (Day 1) visit used to assess eligibility. The baseline value will be considered missing if less than 4 of the 7 days have an assessment.

- Abdominal Pain Intensity (1-10)

- Stool Consistency (day with at least one bowel movement Type 6 or 7)
- Stool Frequency

The baseline value for each of these assessments will be calculated by summing the daily result over the 7-day period and dividing by the number of days with an assessment. The Stool Consistency baseline proportions will be multiplied by 100 to convert to a percentage.

Baseline for the other efficacy assessments is defined as the last non-missing value recorded on or before the Baseline (Day 1) visit.

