## **13. CHANGES TO PROTOCOL SPECIFIED ANALYSES**

The EE analysis set will not be based on all major protocol deviations as indicated in the protocol, but on a subset of the major deviations that are deemed to have significant impact on efficacy data and will be determined in the data review meeting, prior to database lock and prior to unblinding the study.

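### IBS-C stool frequency is a weekly sum in the protocol but a per-assessed-day rate in the SAP, the SAP leaves the baseline scale open, and the change is not declared

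*Protocol*

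**What the plan says.** Protocol 7.1 (Clinical Assessments, Bristol Stool Chart): "Stool frequency will be defined as a sum of weekly CSBMs". Protocol 3.2 sets the Cohort C stool criterion: "Increase of 1 or more Complete spontaneous bowel movements (CSBM) per week compared with baseline". Protocol 10.7 accepts a week with four daily records and gives no rescaling rule for CSBMs.

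SAP 10.1.1 keeps the threshold: "Improvement is defined as an increase of 1 or more complete spontaneous bowel movements (CSBMs) per week compared with baseline". For the weekly value, however, the denominator "will be the number of days with an assessment during the week", and then: "The stool frequency will be multiplied by 7 to convert to a stools per week figure". SAP 10.4 also requires at least 4 days in a week.

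SAP 10.2 derives the baseline by "summing the daily result over the 7-day period and dividing by the number of days with an assessment" and treats it as missing only when fewer than 4 of the 7 days have an assessment. It states a scaling step for stool consistency (times 100) but none for stool frequency.

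SAP 13 lists one departure from the protocol: "The EE analysis set will not be based on all major protocol deviations as indicated in the protocol". The stool frequency rule is not mentioned.

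**The concern.** A sum and a rate are the same number only when every day of the week is recorded, and both documents accept treatment weeks with fewer. A gain of at least 1 CSBM is one of the two conditions for a Cohort C responder week, and one reclassified week can move a subject from 3 to 4 improved weeks of 8, which is the cut for overall response. A programmer following protocol 7.1 and one following SAP 10.1.1 could therefore count different responders.

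The baseline adds a second ambiguity. Read literally, SAP 10.2 produces a daily mean, which would then be compared with a weekly figure. The reader of the SAP is not told that either matter departs from the protocol.

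**Working it through.** **The plan's own figure.** The sample size statement (125 per arm, 40% against 55%, one-sided 10%, Pearson with Yates) promises at least 80% power. Exact binomial enumeration gives 82.5%, so it is met. It does not depend on the point below.

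**Inputs.** Threshold +1 CSBM per week (protocol 3.2, SAP 10.1.1). Entry with fewer than 3 CSBMs in 7 days (protocol 5.1), so the baseline count b is 0, 1 or 2. Minimum 4 of 7 days in a treatment week (protocol 10.7, SAP 10.4) and at baseline (SAP 10.2 only).

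**Rules.** Let b be the CSBMs on d0 baseline days, and c the CSBMs on d treatment days.

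- Sum (protocol 7.1): improved if c − b ≥ 1.
- Rate (SAP 10.1.1, with baseline also multiplied by 7): improved if 7c/d − 7b/d0 ≥ 1.

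**Complete baseline (d0 = 7), incomplete treatment week.** Over b = 0-2 and d = 4-6 the rules disagree once: b = 2, d = 4, c = 2. The sum gives 2 − 2 = 0 (not improved); the rate gives 3.5 − 2 = +1.5 (improved). At 5 days, 2 CSBMs give 2.8 − 2 = 0.8, and at 6 days 2.33 − 2 = 0.33, so both rules say no.

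**Incomplete baseline, full treatment week.** CSBMs needed are b + 1 under the sum, and 7b/d0 + 1 rounded up under the rate:

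| b | Baseline days | Sum | Rate |
|---|---|---|---|
| 1 | 6, 5 or 4 | 2 | 3 |
| 2 | 6 | 3 | 4 (7 × 2/6 + 1 = 3.33) |
| 2 | 5 | 3 | 4 (7 × 2/5 + 1 = 3.8) |
| 2 | 4 | 3 | 5 (7 × 2/4 + 1 = 4.5) |

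With b = 0 both rules need 1.

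**Size for an affected subject (assumptions mine).** Poisson counts, baseline truncated to below 3, no true change, eight full treatment weeks. The outcome is the stool component met in at least 4 of 8 weeks. Worked case: 1.5 per week and a 6-day baseline.

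- Baseline mean 1.5 × 6/7 = 1.286, so b = 0, 1, 2 have weights 0.321, 0.413, 0.266.
- The chance that a week reaches 1, 2, 3 or 4 CSBMs is 0.777, 0.442, 0.191, 0.066. The chance of this in at least 4 of 8 weeks is 0.983, 0.505, 0.0485, 0.001.
- Sum: 0.321 × 0.983 + 0.413 × 0.505 + 0.266 × 0.0485 = 0.54.
- Rate: 0.321 × 0.983 + 0.413 × 0.0485 + 0.266 × 0.001 = 0.34.

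| True CSBMs per week | Complete baseline, either rule | 6-day baseline, sum | 6-day baseline, rate |
|---|---|---|---|
| 1 | 40% | 44% | 39% |
| 1.5 | 50% | 54% | 34% |
| 2 | 62% | 66% | 34% |
| 2.5 | 76% | 79% | 44% |

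The gap runs from 5 to 35 points. Losing one baseline day raises the sum's figure by about 3-4 points. From 1.5 per week upward, most of the gap is the fall under the rate, which comes from rounding up to whole stools.

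**Literal SAP 10.2 (no multiplication by 7 at baseline).** A subject with 2 CSBMs in 7 days at baseline and again on treatment shows 2 − 2/7 = +1.71 and counts as improved with complete data. In the worked case, the literal reading gives 66%, above the sum (54%) instead of below it.

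**The case against.** The strongest reply is that the SAP fills a gap and contradicts nothing. Protocol 7.1 sits under assessments and says nothing about missing days, protocol 3.2 states the criterion per week, and protocol 10.4 leaves detail to the SAP. A rate also fits the reason given in the version 2.0 change log for moving IBS-D from a number to a proportion of days. This is a fair reading, and it supports keeping the rate. It does not supply the missing baseline scale, and it does not explain why a changed component of a primary endpoint is absent from SAP 13.

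It is also fair that incomplete baselines drive the size. Protocol 4.2.1 asks for daily entries over 7 days before Visit 1, and only SAP 10.2 accepts 4 of 7. The documents do not say how often this happens.

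A reader might infer that the rule could be chosen after results are seen. The documents do not support this: SAP 10.1.1 fixes the treatment-week rule, and SAP 6 says that the analyses were defined before lock and unblinding and that later ones are post hoc. A reader might also infer bias between arms. None is shown, since baseline gaps arise before randomisation and the same rule applies to both arms.

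**Conclusion.** The inconsistency stands, with limited reach. With the baseline on a weekly scale, the rules agree on complete data, and with a complete baseline they part in a single configuration. They part more widely for subjects with 4-6 baseline days and at least one baseline CSBM, where the rate is stricter by 1-2 CSBMs in a full week.

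The gaps of 5 to 35 points apply to an affected, unchanged subject with a 6-day baseline, under Poisson counts and for the stool component alone. It would be wrong to read them as shifts in the Cohort C response rate. That effect is smaller, because only subjects with missing days are affected and pain must improve in the same week. It cannot be computed without a missing-diary rate. The unstated baseline scale in SAP 10.2 matters even with complete diaries and decides the direction of the difference, so it is the part that most needs settling.

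**What to change.** Use one rule, CSBMs per day with an assessment multiplied by 7, for the baseline week and every treatment week.

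1. Edit SAP 10.2 so that the stool frequency baseline is also multiplied by 7. SAP 10.1.1 already does this for treatment weeks.
2. List the departure from the protocol 7.1 sum in SAP 13 before unblinding.
3. Optionally, run the raw sum once as a sensitivity analysis of the Cohort C primary endpoint.

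The fix can sit in the SAP. According to the version 3.1 change log, all patients had been randomised and had completed the primary assessments, so rewording protocol 7.1 would not alter conduct.

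The cost is two sentences and at most one table. The downside is that the rate is noticeably stricter than the sum for subjects with an incomplete baseline and at least one baseline CSBM, so the Cohort C response rate may be somewhat lower.
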